11.0 Data and Specimen Management

11.1 Data analysis plan.

- A. **Data management.** We will use data management methods in place for our ongoing NHBLI-funded PAD studies. Data from baseline and follow-up study visits are acquired on paper forms and processed using the Teleform system by Cardiff Software. We have successfully used this system for over 8,000 patient visits in our previous and ongoing studies. Data are backed-up on multiple hard drives and copied to CDROM for secure off-site storage.
- B. **Data Safety Monitoring Board (DSMB).** We have identified nationally recognized experts to serve on the DSMB.

Statistical Analyses. Analyses will be performed according to the intention to treat principle. Data will be analyzed according to each participant's originally assigned group, irrespective of whether the participant adheres to his/her assignment. Prior to analyses, the distributions of the variables (changes) will be examined and necessary transformations will be performed. The balance of socio-demographic factors and prognostic factors (such as age, sex, race, ABI, comorbidities, and relevant medication use) will be compared between the three groups using ANOVA or chi-square tests. If there is any indication of major imbalance, proper analysis of covariance adjustments will be performed in data analyses.

NOTE: The original plan to use two sample two-tailed t-tests was changed to a mixed model for repeated measures analysis on 8/27/2020 prior to analyzing any data. This change was made because as of 8/27/202, investigators are projecting an approximately 16% loss to follow-up rate at 52 week follow-up. The mixed model for repeated measures will be used to adjust for missing data.

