For our Primary Aim, we will use mixed model for repeated measures (MMRM) analysis to compare changes in six-minute walk performance at 52-week follow-up between the low vs. the high-intensity exercise group and between the low-intensity exercise group vs. the control group, respectively. To this end, the 26-week and 52-week changes of six-minute walk from baseline are treated as correlated outcomes, and independent variables include visit (26-week and 52 week), treatment (low-intensity, high-intensity, control), visit/treatment interactions and baseline six-minute walk performance. Unstructured variance-covariance matrix will be used to model the within-person correlations. In addition, we will also adjust for potentially imbalanced baseline confounders such as age, sex and baseline six-minute walk performance. When there is evidence that the normality assumption for the distribution of measures of interest is severely violated, we will perform Wilcoxon rank-sum test for the comparison. The nonparametric adjustment for the imbalance in mean difference of baseline covariates will be employed, when needed.

PROTOCOL TITLE: Low InTensity Exercise intervention in PAD: The LITE Trial

For Secondary Aim #1, we will use MMRM analysis to compare changes in six-minute walk, physical activity, and SF-36 PF and WIQ distance and speed scores at 26-week follow-up between the low- and high-intensity exercise groups and between the low-intensity exercise and control group, respectively.

For our Secondary Aim #2, we will use MMRM analysis to compare changes in maximal treadmill walking time, physical activity, and SF-36 PF and WIQ distance and speed scores at 52-week follow-up between the low- and high-intensity exercise groups and between the low-intensity exercise and control groups, respectively.

For our Secondary Aim #3, we will use normal approximation for binomial distribution to compare the proportion of participants who achieve adherence (as defined in section C18) between the low vs. high intensity exercise groups. We will also use logistic regression to compare the adherence rate between these two groups, adjusting for potentially imbalanced baseline confounders such as age, sex, and baseline six-minute walk performance. We will also use two sample two-tailed t-tests to compare adherence to the exercise intervention overall and at the prescribed intensity between the high vs. low intensity groups at 52-week follow-up.

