For our Secondary Aim #4, we will use MMRM analysis to compare changes in six-minute walk distance, physical activity, and SF-36 PF and WIQ distance and speed scores at 26-week follow-up between the high-intensity exercise and control groups.

For our Secondary Aim #5, we will use MMRM analysis to compare changes in six-minute walk distance, maximum treadmill walking time, physical activity, and SF-36 PF and WIQ distance and speed scores at 52 week follow up between high intensity exercise and control groups.

For our Secondary Aim #6, we will use two sample two-tailed t-tests to compare changes in COX, citrate synthase, and mitochondrial DNA at 52-week follow-up between the low intensity vs. the high-intensity exercise group and between the low-intensity exercise and control groups. We will also compare change in nitrotyrosine muscle measurements between the high-intensity exercise and the control groups. We will repeat these comparisons for the participants who adhere to their prescribed exercise intensity, measured by the ActiGraph.

For our Exploratory Aim #1, we will use two sample two-tailed test compare patients' perception to exercise at 52-week follow-up between high and low-intensity groups. For our Exploratory Aim #2, we will evaluate the effect of modified combo intervention (weight loss + LITE home-based exercise) on six-minute walk distance at approximately 12 week follow-up. This pilot study was completed in 2018.

The significance level for the Primary Aim will be 0.05/2 to adjust for two comparisons between low-intensity and high-intensity arms and between low-intensity and control arms.

The significance level will be 0.05 for all secondary aims. Furthermore, Secondary Aims #4 and #5 were pre-specified but added after the LITE Trial was underway in response to two negative trials of home-based exercise in patients with PAD demonstrating that a high-intensity walking exercise program did not improve six-minute walk or other outcomes in people with PAD (5, 6).

PROTOCOL TITLE: Low InTensity Exercise intervention in PAD: The LITE Trial

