Power estimates. For all primary and secondary aims, we anticipate a 15% drop-out rate at 52-week follow-up, based on 12-month follow-up rates in our GOALS and SILC trials (52,55). We will randomize 305 participants. Of these, 120 will be randomized to the low-intensity intervention, 120 will be randomized to the high-intensity exercise intervention, and 65 will be randomized to the control group. We will enroll more participants in each exercise group than the attention control group because we anticipate that the effect size of the low vs. high intensity exercise comparison will be lower than the effect size of the low intensity vs. the control group. For our Primary Specific Aim, we will have 80% power to detect a minimum difference of 0.43 standard deviations (SD) between the low intensity vs. high intensity exercise groups and a difference of 0.52 SD between the low-intensity and the attention control groups, in change of six-minute walk distance at 52-week follow-up, using two-sided two-sample t-tests **with a significance of 0.025 to adjust for the two comparisons.** Low intensity exercise will be considered effective if either comparison (i.e. with high intensity exercise or with the attention control group) is statistically significant. The SD of the change in six-minute walk in our GOALS and SILC trials was approximately 60 meters. Therefore, our sample size allows us to detect a difference in change in six-minute walk of 26 meters and 31 meters, respectively, between the low vs. high intensity groups and between the low intensity and control groups. Prior studies have defined clinically meaningful changes in the six-minute walk as 30 meters (small meaningful change) and 50 meters (large meaningful change) (102,103). Thus, our power should be adequate to detect a clinically meaningful difference. For our Secondary Aim #1, we will have 80% power to detect a difference of 0.39 SD between the high vs. low intensity exercise interventions and a difference of 0.47 SD between the low-intensity intervention vs. control group, respectively, in changes of six-minute walk, physical activity, WIQ scores, and SF-36 scores at 26 –week follow-up using two-sided two-sample t-tests with a significance of 0.05. For our Secondary Aim #2, we will have 80% power to detect a difference of 0.39 SD between the high vs. low intensity exercise interventions and a difference of 0.47 SD between the low-intensity intervention vs. control group, respectively, in changes of maximal treadmill walking time, physical activity, and WIQ and SF-36 scores at 52-week follow-up, using two-sided two-sample t-tests with a significance level of 0.05. In our SILC trial, the observed differences between the intervention and control groups are 0.61 SD, 0.59 SD and 0.61 SD in changes of maximal treadmill walking time, WIQ distance, and SF-36 physical functioning scores, respectively (52). In a study by Gardner et al of supervised exercise in participants with PAD (73), the observed improvement in physical activity

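### Beyond baseline six-minute walk, covariates in the primary model depend on baseline balance tests or are left unclear, so the decisive model is not fixed and precision is forgone

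*Combined protocol and SAP*

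**What the plan says.** Three parts of the combined protocol and SAP bear on this.

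- **Section 11.1, Statistical Analyses, opening paragraph.** Demographic and prognostic factors (age, sex, race, ABI, comorbidities and medication are given as examples) are tested across the three arms by ANOVA or chi-square. Then: "If there is any indication of major imbalance, proper analysis of covariance adjustments will be performed in data analyses". The paragraph does not define a major imbalance, close the list, or say whether the adjusted model replaces the unadjusted one.
- **Section 11.1, Primary Aim paragraph.** The MMRM contains visit, treatment, their interaction and baseline six-minute walk, with no condition attached. It continues: "In addition, we will also adjust for potentially imbalanced baseline confounders such as age, sex and baseline six-minute walk performance". Baseline walk is thus named twice, and it is not said whether age and sex are always in the model. The rank-based fallback also adjusts only if required.
- **Section 3.1 C, Randomization.** Allocation is stratified by eligibility for, and consent to, muscle biopsy. The MMRM description does not name this factor.

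On the decision level, section 11.1 states: "The significance level for the Primary Aim will be 0.05/2 to adjust for two comparisons". It does not say which covariate set that level applies to. By contrast, section 9.2 X says that analyses will be repeated if medication changes or revascularisation are unbalanced after randomisation. That reads as an additional analysis; the baseline rule carries no such label.

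**The concern.** Under randomisation every baseline difference is due to chance, so a balance test has a null hypothesis that is true by design. It says nothing about whether a covariate predicts change in walking distance. A predictive covariate is left out when it happens to balance, and its variance reduction is lost. An irrelevant one may come in because it happened not to balance.

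Two things are at stake. One is precision: these covariates are already to be collected and could sharpen both primary comparisons. The other is prespecification: with no threshold and an open list, two analysts could follow section 11.1 faithfully and report different primary models.

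**Working it through.** **Inputs (section 11.2).** "Of these, 120 will be randomized to the low-intensity intervention"; 120 go to high intensity and 65 to control; dropout is 15%; two-sided α is 0.025 per comparison. The detectable differences are 0.43 SD ("we will have 80% power to detect a minimum difference of 0.43 standard deviations (SD) between the low intensity vs. high intensity exercise groups") and 0.52 SD ("a difference of 0.52 SD between the low-intensity and the attention control groups"). The SD of change is 60 m.

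**1. The plan's own figure.** Completers: 120 × 0.85 = 102; 65 × 0.85 = 55.25, taken as 55. Normal approximation, power = Φ(d / √(1/n₁ + 1/n₂) − 2.241):

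- Low vs high: 0.43 / √(1/102 + 1/102) = 3.071; Φ(0.830) = 79.7% (noncentral t: 79.1%).
- Low vs control: 0.52 / √(1/102 + 1/55) = 3.108; Φ(0.867) = 80.7% (noncentral t: 80.0%).
- In metres: 0.43 × 60 = 25.8 and 0.52 × 60 = 31.2, against 26 and 31 stated.

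The figures reproduce and claim no gain from covariates.

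**2. Chance flags.** The plan sets no threshold, so p<0.05 is an assumption. With k independent covariates, P(at least one flagged) = 1 − 0.95^k: 18.5% for k = 4, 26.5% for 6, 33.7% for 8 and 40.1% for 10.

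**3. Precision on offer.** Let R² be the share of variance, after baseline walk, that the extra covariates explain. The documents give no value, so a range is shown. The residual SD is multiplied by √(1 − R²). Noncentral-t power, before the small cost of estimating the covariate effects:

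| R² | Low vs high, 0.43 SD | Low vs control, 0.52 SD | Detectable difference at 80% power |
|---|---|---|---|
| 0 | 79.1% | 80.0% | 26.1 m / 31.2 m |
| 5% | 81.3% | 82.2% | 25.4 m / 30.4 m |
| 10% | 83.5% | 84.3% | 24.7 m / 29.6 m |
| 20% | 87.9% | 88.6% | 23.3 m / 27.9 m |

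**4. What the rule recovers.** Simulated trials with 102/102/55 completers, a linear model for 52-week change, and a covariate added only if its ANOVA p<0.05. Power at R² of 5%, 10% and 20%:

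| Set-up | Adjust if flagged | Always adjust | Gain (points) |
|---|---|---|---|
| Low vs high, 8 covariates, 3 prognostic (12,000 runs) | 79.6 / 79.2 / 79.4% | 81.5 / 82.9 / 87.3% | 1.9 / 3.7 / 7.9 |
| Low vs high, 6 equally prognostic (20,000 runs) | 79.0 / 79.7 / 79.9% | 80.3 / 83.0 / 87.2% | 1.2 / 3.3 / 7.3 |
| Low vs control at 0.52 SD, 6 equally prognostic (12,000 runs) | 79.8 / 79.9 / 81.3% | 80.7 / 83.8 / 88.5% | 0.9 / 3.9 / 7.2 |

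In the second row, never adjusting gives 79.0 / 79.4 / 79.3%, so the rule is almost equivalent to not adjusting.

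**5. Type I error at nominal 2.5%.** Following the rule mechanically gives 2.04–2.62% with eight covariates and R² of 5–20%. The Monte Carlo standard error is √(0.025 × 0.975 / 12,000) = 0.14 points, so 2.62% is not distinguishable from 2.5%. Taking the smaller of the adjusted and unadjusted p-values gives 3.0–3.6%.

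**The case against.** The strongest reply is that the plan already does much of what is asked. Baseline six-minute walk, a natural predictor of change in the same measure, is in the MMRM unconditionally. The sentence naming age and sex mentions no test and also lists the baseline walk, which is already fixed, so age and sex can be read as fixed too. On that reading only ABI and the biopsy stratum would be new. The p<0.05 trigger, the number of covariates and the R² are also assumptions, and a one-endpoint linear model stands in for a two-visit MMRM. All of this stands. It limits the size of the point, but not the point itself: the opening paragraph lists age and sex among the tested factors, and nothing settles which paragraph governs.

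A reader might also infer more than the documents support:

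- **That covariates enter only if flagged.** Baseline walk does not.
- **That the trial is underpowered.** The 80% comes from unadjusted t-tests and reproduces; what is lost is efficiency above that.
- **That type I error is inflated.** This would need a choice between p-values. The documents do not authorise one, and the balance tests use baseline data, not outcomes. The undefined trigger merely fails to exclude it.
- **That Aim 3 adherence is governed by the same rule.** The unadjusted comparison of proportions is listed first. The logistic sentence refers to possible imbalance but names no test.
- **That the covariates were chosen with results in hand.** Section 9.1 does report a trial finding, so this text postdates some analysis. But section 11.1 dates the change to MMRM to before any data were analysed, and nothing shows when the covariate set was settled.

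**Conclusion.** The point holds in limited form. Beyond baseline six-minute walk, adjustment of the primary MMRM is either triggered by balance tests with no threshold or left ambiguous, and the decisive model is not fixed in the text.

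The forgone power is about 2–8 points for low vs high at 0.43 SD and for low vs control at 0.52 SD. This assumes that the extra covariates explain 5–20% of the variance left after baseline walk and that imbalance means p<0.05; at the 5% end the simulated gain is 1–2 points. It also treats the stated effect sizes as being in units of that remaining SD. If baseline walk already removes part of the 60 m, power starts above 80% and there is less to gain. If the covariates explain little, the gain is near zero, but the model is still not fixed.

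The sample size is not in error, and the rule followed as written does not raise type I error. This is a cheap improvement that should be made, not a fatal flaw.

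**What to change.** In section 11.1, replace the imbalance rule with one covariate list for the primary MMRM, used whatever the observed balance: baseline six-minute walk, age, sex, ABI and the biopsy stratification factor from section 3.1 C. Use the matching baseline value, age, sex and ABI in the secondary MMRMs. State that this model decides the Primary Aim at 0.025.

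Drop the balance tests as a trigger and describe baseline characteristics by arm without significance tests. Label any model that adds a covariate because of observed imbalance as a sensitivity analysis that cannot replace the primary result.

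Because section 9.1 already reports a trial finding, a list written now cannot be presented as prospective on its own. The sponsor should document which covariate set was fixed before the analysis, and when.

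The cost is wording and a few degrees of freedom. The covariates are already part of the planned data.

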Missing data occur when participants are lost to follow-up. First, we will make every effort to ensure that participants return for the 52-week follow-up. We will use proxies to help us locate participants we are unable to reach and we will mail reminder letters when participants are not responsive to telephone calls. We will encourage participants who do not adhere to their assigned groups to return for the 52-week follow-up by providing transportation and monetary incentives. Thus, we anticipate that the proportion of participants without 52-week follow-up data will be small. Second, MMRM analysis is valid under the missing at random assumption. In case the proportion of missing data at 52-week follow-up is not small (>25%), we will additionally employ the multiple imputation approach to account for missing data as sensitivity analysis. If there is evidence for the possibility of missing not at random, we will perform additional analyses using pattern-mixture and shared-parameter models (105).

11.2 Power analysis.

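### On evidence of severe non-normality, the plan hands the primary comparison to a rank-sum test and so loses the missing-data handling for which MMRM was adopted

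*Combined protocol and SAP*

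**What the plan says.** All of this is in section 11.1 (Data analysis plan) of the combined protocol and SAP.

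- **Why MMRM.** A dated note (8/27/2020) replaces t-tests with MMRM because "investigators are projecting an approximately 16% loss to follow-up rate at 52 week follow-up". It ends: "The mixed model for repeated measures will be used to adjust for missing data".
- **Primary model.** In the Primary Aim paragraph, "the 26-week and 52-week changes of six-minute walk from baseline are treated as correlated outcomes", with an unstructured covariance matrix and the baseline walk as a covariate.
- **Fallback.** The same paragraph provides for the case where the "normality assumption for the distribution of measures of interest is severely violated, we will perform Wilcoxon rank-sum test for the comparison". The only adjustment attached to it concerns baseline covariates: "The nonparametric adjustment for the imbalance in mean difference of baseline covariates will be employed, when needed".
- **Transformation.** Before any of this, "the distributions of the variables (changes) will be examined and necessary transformations will be performed". The sentence covers outcomes in general and does not exempt six-minute walk.
- **Missing data.** The plan states that "MMRM analysis is valid under the missing at random assumption" and makes no such statement for the rank-sum test. Above 25% missing at 52 weeks, "we will additionally employ the multiple imputation approach to account for missing data as sensitivity analysis". Pattern-mixture and shared-parameter models are further analyses, used if data missing not at random are suspected.

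The plan does not say what counts as severe violation, who decides, whether the MMRM stays primary once the fallback is used, or how a missing 52-week walk enters the rank-sum test.

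**The concern.** A two-sample rank-sum test on 52-week change needs an observed 52-week walk and makes no use of the 26-week walk. Without imputation it is a complete-case test. Using it for the primary comparison would undo the stated purpose of the August 2020 change, and the choice would be made after inspecting the outcome distribution, without a criterion.

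Two things are at stake. The first is validity: if the participants lost differ between arms in how they were walking at 26 weeks, a complete-case comparison can be shifted even when the MMRM is not. The second is interpretation: section 11.2 sets the trial against meaningful changes of 30 m and 50 m, and a transformed change cannot be read directly on that scale.

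**Working it through.** **The plan's own figure.** Section 11.2 gives 120, 120 and 65 randomised, 15% dropout, an SD of change of 60 m, two-sided alpha 0.025, and 80% power for 0.43 SD (low v high) and 0.52 SD (low v control). Completers are 120 × 0.85 = 102 and 65 × 0.85 = 55.25. Power = Φ(d√(n₁n₂/(n₁+n₂)) − 2.2414).

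- Low v high: 0.43 × √(102 × 102/204) = 3.071, and Φ(0.829) = 79.7%.
- Low v control: 0.52 × √(102 × 55.25/157.25) = 3.113, and Φ(0.872) = 80.8%.

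The noncentral t gives 79.1% and 80.1%. In metres, 0.43 × 60 = 25.8 and 0.52 × 60 = 31.2, matching the stated 26 and 31. The plan's figures reproduce, and nothing here disputes them.

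**Who enters the fallback.** At 16% loss, 0.16 × 305 = 48.8, so about 49 participants lack a 52-week walk and about 256 would enter the rank-sum test. Imputation needs more than 0.25 × 305 = 76.25 missing, so 49 would not trigger it.

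**Why the two methods differ.** Take two visits, with dropout only after week 26. The likelihood estimate of the 52-week difference is b₁ + b₂d₂₆. Here b₁ and b₂ are the coefficients of arm and 26-week change among those seen at both visits, and d₂₆ is the difference in mean 26-week change among everyone. Dropouts contribute through d₂₆. The rank test has no such term. For normal data it carries a shift of about ρ × g, where ρ is the 26/52-week correlation and g is the gap in 26-week change that dropout creates between the arms' completers.

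**Simulation.** From the plan: SD 60 m, 120 v 120, 16% missing at 52 weeks, alpha 0.025. Assumed, because the documents do not give them: ρ of 0.5 or 0.7, dropout logistic in the 26-week change, every dropout having a 26-week walk, and lognormal-type skew for the skewed case. The true difference is 0. There were 1,500 runs per cell, so the Monte Carlo standard error near 2.5% is √(0.025 × 0.975/1500) = 0.4 points. The likelihood estimate stands in for the MMRM, without the baseline covariate. Each cell gives the result for ρ = 0.5, then ρ = 0.7. Shift is the Hodges-Lehmann estimate among completers.

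| Dropout log-odds per SD (low, high) | Normal: shift, m | Normal: rank-sum | Normal: likelihood | Skewed: shift, m | Skewed: rank-sum | Skewed: likelihood |
|---|---|---|---|---|---|---|
| 0, 0 | −0.1; −0.2 | 2.3%; 2.9% | 2.1%; 3.1% | 0.1; 0.2 | 2.4%; 2.5% | 2.5%; 2.5% |
| −0.5, −0.5 | 0.2; 0.1 | 2.7%; 2.9% | 3.2%; 3.3% | 0.0; −0.1 | 2.2%; 2.3% | 2.7%; 2.7% |
| 0, −1 | −4.6; −6.5 | 4.7%; 6.3% | 1.9%; 2.3% | −1.5; −2.1 | 2.6%; 3.5% | 2.1%; 1.9% |
| −0.5, +0.5 | 4.8; 6.7 | 5.3%; 8.0% | 3.0%; 2.3% | 2.1; 2.8 | 3.7%; 6.5% | 2.7%; 2.3% |
| −1, +1 | 8.5; 11.6 | 10.9%; 20.1% | 2.6%; 2.7% | 3.7; 4.8 | 8.5%; 12.0% | 3.1%; 2.5% |

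The shifts behave as ρ × g predicts: 4.8/0.5 and 6.7/0.7 both give g of about 9.6 m, and 8.5/0.5 = 17.0 agrees closely with 11.6/0.7 = 16.6. A separate set of runs under assumptions of the same kind gave about 3% to 17% under arm-differential dropout (about 2.5% to 5.5% when only one arm's dropout depended on outcome), with the likelihood estimate at about 2% to 3%.

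**Power where the fallback applies.** With outcome-unrelated dropout and a true 26 m shift, rank-sum v likelihood power is about 76–77% v 80–83% for normal data, 95–97% v 84–85% for t with 3 degrees of freedom, and over 99% v 83% for lognormal skew.

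**The case against.** The strongest objection is that the fallback is a named contingency with a narrow trigger, and that in that situation it is often the sharper test. That much stands. A reader might infer that the rank test costs power. The documents do not support this: the plan invokes the test only under severe non-normality, where the runs above favour it for a location shift. Its power deficit appears only with normal data.

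A reader might also infer that the primary result would be biased. The documents give no dropout by arm and no relation between dropout and walking. The protocol argues that pain deters exercise (section 2.2) and prescribes pain in one exercise arm only (section 9.2). That makes differential dropout conceivable but does not establish it. Shifts are also smaller with skewed data, the more relevant setting, than with normal data.

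Three limits of wording stand. The trigger is severe violation, not any departure from normality. That the MMRM is replaced, and that the rank test uses completers only, are inferences from the text, though natural ones. And nothing indicates that a transformation is expected for six-minute walk.

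The other missing-data provisions do not answer the point. Imputation would not be triggered at 16% and is a sensitivity analysis in any case, and the models for data missing not at random need separate evidence and are additional. Neither changes how the rank-sum comparison treats missing walks.

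**Conclusion.** The point holds, conditionally. As written, the rule can move the primary comparison to a method without the missing-data handling that justified the MMRM, on a judgement with no stated criterion.

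Under no true effect and arm-differential dropout, rank-sum type I error is roughly 3% to 17% at a nominal 2.5%, and about 3% to 12% with skewed data, where shifts are about 1 to 5 m. The one cell at 20.1% needs a correlation of 0.7 and strong, opposite dropout in the two arms, so the top of the range depends on the assumptions. Inflation is essentially absent when dropout is unrelated to outcome or equally related in both arms.

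The MMRM's advantage also assumes that those lost have a 26-week walk; anyone lost before week 26 contributes no post-baseline information to either method. Non-normality alone did not upset the likelihood test here: it rejected 1.9% to 3.1% across the skewed cells. That was checked at 120 v 120 only, not against the smaller control arm.

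This is a cheap improvement. It is not evidence that a reported result is wrong.

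**What to change.** In section 11.1:

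1. State that the MMRM on the metre scale remains the primary analysis whatever the distribution, with sandwich or bootstrap standard errors if residuals are clearly non-normal.
2. Make the rank test a sensitivity analysis, baseline-adjusted and run on multiply imputed data whatever the proportion missing.
3. Exempt the primary six-minute walk analysis from the general transformation step, so that it stays readable against 30 m and 50 m.

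Section 9.1 already describes a trial finding. If the analysis has been run, the equivalent step is to report the MMRM estimate in metres and say whether any transformation or the fallback was used.

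The cost is a few sentences and one sensitivity run. The downside is some loss of power and more sensitivity to outliers under heavy tails or skew, which the rank sensitivity analysis would show.

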19.0 Setting

The research will be conducted at Northwestern Memorial Hospital, [name], and [name]. If a participant is unable or unwilling to come back to our site for a follow-up visit or if they are unable or unwilling to come to the medical center for an intervention visit, we may go to their home to collect follow-up data or carry out the intervention visit.

Exercise intervention sessions will be conducted at either L.A. Fitness ([name] or [name]) or at [name]. Health education sessions will take place at 750

PROTOCOL TITLE: Low InTensity Exercise intervention in PAD: The LITE Trial

[name].

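### Aim 6 leaves the baseline biopsy value out of its t-tests on change, and for treadmill time a single-visit MMRM brings in no 26-week data: a minor precision and wording point for secondary aims

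*Combined protocol and SAP*

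**What the plan says.** Table 4 (Section 9.1) schedules treadmill performance and calf muscle biopsy at baseline and 52 weeks, with nothing at 26 weeks. The rest of the document agrees. The 26-week aims (#1 and #4) omit treadmill time, Section 9.2 S repeats the biopsy at 52 weeks, and Section 11.2 places treadmill change at 52 weeks only.

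Section 11.1 then sets these analyses:

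- Aim #6: "we will use two sample two-tailed t-tests to compare changes in COX, citrate synthase, and mitochondrial DNA at 52-week follow-up". No covariate is named.
- General rule on adjustment: "If there is any indication of major imbalance, proper analysis of covariance adjustments will be performed in data analyses". The examples given are socio-demographic and prognostic factors. Baseline muscle measures are not among them.
- Aim #2, which includes treadmill time: "we will use MMRM analysis to compare changes in maximal treadmill walking time, physical activity, and SF-36 PF and WIQ distance and speed scores". Aim #5 uses MMRM for treadmill time in the same way. No covariates are listed for either.
- The MMRM is set out in full only for the Primary Aim. Its model terms include "visit/treatment interactions and baseline six-minute walk performance".
- Reason for the move from t-tests to MMRM in August 2020, when about 16% loss to follow-up was projected: "The mixed model for repeated measures will be used to adjust for missing data".
- Sensitivity analyses: "In case the proportion of missing data at 52-week follow-up is not small (>25%), we will additionally employ the multiple imputation approach", and separately "If there is evidence for the possibility of missing not at random, we will perform additional analyses using pattern-mixture and shared-parameter models".

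Section 19.0 adds that, for participants who cannot or will not return to the site, "we may go to their home to collect follow-up data or carry out the intervention visit".

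**The concern.** Aim 6 contains the trial's smallest comparisons: 50 participants per arm, each measurement needing an invasive biopsy. A t-test on change fixes the coefficient of the baseline value at one. ANCOVA estimates that coefficient and, in large samples, is never less precise. The only route to adjustment in the plan depends on seeing imbalance, so precision that is already paid for may go unused.

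For treadmill time the issue is what the stated rationale can deliver. An MMRM helps with dropout because a participant's earlier post-baseline value of the same outcome informs the missing later one. Treadmill time has no earlier post-baseline value. A reader of Section 11.1 could believe that the treadmill comparison uses 26-week data to handle dropout, which it cannot.

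**Working it through.** **1. The plan's figures reproduce.** Inputs from Section 11.2: 50 per arm for Aim 6, 120 per exercise arm, 15% dropout, 80% power, two-sided 0.05.

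- Aim 6: 50 × 0.85 = 42.5 per arm. (1.960 + 0.842) × √(2/42.5) = 0.608 SD by normal approximation, and 0.615 by noncentral t. The plan states 0.61.
- Aim 2, low vs high intensity: 120 × 0.85 = 102 per arm gives 0.394 SD. The plan states 0.39.

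The arithmetic is sound. The question is the choice of method.

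**2. ANCOVA against change score, Aim 6.** Let r be the baseline-to-52-week correlation and k the ratio of the 52-week SD to the baseline SD. Neither is in the documents, so both are assumptions here.

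Var(ANCOVA) / Var(change) = k²(1 − r²) / (1 + k² − 2rk), which is (1 + r)/2 when k = 1.

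With N = 85 analysed, estimating the slope multiplies this by (N − 3)/(N − 4) = 82/81 and costs one degree of freedom. The detectable difference is 0.615 times the square root of the result.

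| r (k = 1) | Variance ratio, large sample | Detectable difference at N = 85 | Equivalent to |
|---|---|---|---|
| 0.3 | 0.65 | 0.50 SD | 52% more biopsies |
| 0.5 | 0.75 | 0.54 SD | 32% |
| 0.7 | 0.85 | 0.57 SD | 16% |
| 0.8 | 0.90 | 0.59 SD | 10% |
| 0.9 | 0.95 | 0.60 SD | 4% |

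For example, at r = 0.3: 0.615 × √(0.65 × 82/81) = 0.499.

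Unequal variances move this either way:

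- k = 0.8, r from 0.3 to 0.8: 0.44 to 0.50 SD.
- k = 1.25, r from 0.3 to 0.8: 0.55 to 0.62 SD. At r = 0.8 the large-sample ratio is 1.5625 × 0.36 / (1 + 1.5625 − 2.0) = 0.5625/0.5625 = 1.00, so there is no gain (0.619 against 0.615 once the slope is estimated).

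**3. MMRM with one post-baseline visit.** Each participant supplies at most one record, so there is no within-person covariance to estimate. The fit is least squares among those tested at 52 weeks, and it is an ANCOVA only if baseline treadmill time is in the model.

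Compare an outcome measured at both visits, with a fraction m missing at 52 weeks and 26-week data complete. In units of σ²/n, the complete-case variance is 1/(1 − m) and the likelihood-based variance is (1 − ρ²)/(1 − m) + ρ², where ρ is the 26-to-52-week correlation. The share of lost information recovered is therefore ρ²: 9%, 25% and 49% for assumed ρ of 0.3, 0.5 and 0.7. For treadmill time it is zero.

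**4. Would the imputation trigger be met?** 0.25 × 305 = 76.25, so at least 77 missing tests are needed. Projected loss is 0.16 × 305 = 48.8, about 49. The other 28 would have to come from the 305 − 49 = 256 still followed (28/256 = 11%), seen without a treadmill test, for instance at home. The documents do not give this number.

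**5. Illustrative treadmill bias among completers.** Simulation with 120 per arm, no true effect, 2,000 replicates. Assumed correlations with treadmill change are 0.5 for 26-week status and 0.6 for 52-week status, with 0.7 between the two statuses. The log-odds of missingness are 1 per SD. Bias is in SD of treadmill change, with Monte Carlo error 0.003:

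- 16% loss in both arms: 0.000.
- 14% vs 18%: 0.014.
- 10% vs 22%: 0.053.
- 16% in both arms plus home follow-up without a test (19% vs 25% missing in total): 0.043.

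The plan's detectable difference for this comparison is 0.39 SD.

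**The case against.** The strongest reply is that nothing here is an error. Under randomization a t-test on change is valid, and the Aim 6 analysis and power calculation agree with each other. The effects cited in Section 11.2 as benchmarks (0.75 to 3.17 SD) all exceed 0.61. The ANCOVA gain rests entirely on a correlation and an SD ratio that the documents do not give, and it can be nil. All of that stands, and it limits the point to precision.

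On treadmill time, Section 11.1 describes the MMRM once and then uses the name as shorthand. Physical activity, WIQ and SF-36 have no own-baseline covariate named either. The natural reading is that each outcome takes its own baseline, so the treadmill gap is a missing detail shared by every non-primary MMRM outcome, not a defect peculiar to it. The plan also never says that 26-week values recover treadmill tests. It says that MMRM adjusts for missing data and is valid under missing at random. A single-visit model remains valid if missingness depends only on arm and the covariates in the model. What survives is narrower: no 26-week information enters the treadmill comparison.

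A reader might go further and infer that the treadmill result is biased by dropout. The documents do not support that. The larger simulated values need missingness that depends on follow-up status and differs between arms. The plan projects neither, and the home-visit provision in Section 19.0 gives no numbers and does not mention treadmill testing.

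Finally, Section 9.1 already reports the main finding as known, so an extra analysis adds flexibility across several biomarkers, each tested at 0.05. That is a fair cost, and it is met by keeping the t-test as the reference.

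**Conclusion.** The point holds as a minor improvement to secondary aims. Aim 6 can be adjusted for a value already collected. On equal variances and assumed r of 0.3 to 0.9, the detectable difference falls from about 0.61 to 0.50–0.60 SD, with no gain at an SD ratio of 1.25 and r of 0.8. It would be wrong to infer that the Aim 6 tests are invalid or underpowered: they meet the plan's own target.

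For treadmill time, it follows from the schedule alone that a participant without a 52-week test contributes nothing to the treatment comparison, so the missing-data rationale should not be read as bringing in 26-week data for it. The practical consequence is probably small: at most 0.053 SD in the scenarios tried, against a detectable 0.39 SD, and zero under equal 16% loss. The primary analysis and the Aim 2 and Aim 6 power figures are untouched.

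**What to change.** - Aim 6: keep the pre-specified t-test and report beside it an ANCOVA of the 52-week (or change) value on arm and the same measure's baseline value. State that the t-test remains the reference if the two disagree. Label the ANCOVA as added after results if that is so for these outcomes.
- Treadmill time (Aims #2 and #5): state that the model has one post-baseline visit and uses baseline treadmill time as covariate. One clause giving each MMRM outcome its own baseline would cover the other outcomes too.
- Limit the missing-data sentence in Section 11.1 to outcomes measured at both 26 and 52 weeks.
- Report, by arm, how many participants have no 52-week treadmill test, separating those lost from those followed without a test.
- Optional: a sensitivity analysis by multiple imputation within arm, using baseline treadmill time and the 26- and 52-week six-minute walk, activity, WIQ and SF-36 data, whether or not the 25% threshold is reached. In the simulated home-visit scenario, adding the 52-week measures reduced the bias from 0.024 (26-week data only) to 0.006 SD.

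The cost is one added model for the biopsy outcomes, a count and some wording. If the optional analysis is done, an imputation model must also be specified. No new data are needed.
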